Subcutaneous administration of dalantercept once every 3 weeks in this study was generally well tolerated. Treatment-related SAEs occurred in 5 patients including 3 patients with fluid overload and/or congestive heart failure (CHF), 1 patient with LV dysfunction, and 1 patient with fatigue. Adverse events (AEs) observed with increased frequency at higher dose levels included peripheral edema, anemia, epistaxis, and telangiectasia. The AEs of epistaxis and telangiectasia may be related to the mechanism of action of dalantercept on angiogenesis, leading to dilated vessels in the skin. Dose-dependent fluid retention manifested as peripheral edema, dyspnea, and weight gain, responded to diuretic therapy. Dalantercept treatment resulted in a dose-dependent decrease in red blood cells (RBC) and hemoglobin levels, with no evidence of hemolysis or hemorrhage. No significant, dose-related events of hypertension, GI perforation, or proteinuria have been observed in the study to date, indicating a safety profile that appears distinct from VEGF-inhibitors. Due to toxicities observed at higher doses, patients in the dose expansion cohort were treated with 1.6 mg/kg.

Dalantercept is also being evaluated in an on-going Phase 2, open-label study in patients with recurrent or metastatic squamous cell carcinoma of the head and neck (SCCHN, A041-03) who have been previously treated with at least one platinum-containing regimen. The primary objective is to estimate the objective response rate (ORR) in this population. Secondary objectives include safety and tolerability and pharmacokinetic (PK) profile of dalantercept as well as evaluate progression free survival (PFS), overall survival (OS), time to tumor progression (TTP), duration of response, and rate of disease control (ORR + stable disease [SD]). In addition, the study will explore association of the expression of BMP9/10, ALK1 and/or other

relevant markers in tumor tissue and blood with tumor response and/or other assessments of clinical response and pharmacodynamic (PD) biomarkers. The dalantercept IB should be reviewed prior to initiating the study for the most current information.

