### **7.5. Potential Risks of Human Use of Axitinib**

The most common side effects observed in more than 20% of patients who have taken axitinib include diarrhea, hypertension, fatigue, decreased appetite, nausea, dysphonia, palmar-plantar erythrodysesthesia (hand-foot) syndrome, weight decreased, vomiting, asthenia, and constipation. For additional risks associated with patients taking axitinib, please refer to the axitinib prescribing information (see Inlyta® [axitinib] prescribing information, *Warnings and Precautions*).

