## 9.2. Discussion of Study Design

### 9.2.1. Study Design Rationale

Dalantercept was tested in the A498 and the 786-O RCC mouse tumor models, both as monotherapy and in combination with sunitinib. In the monotherapy studies, dalantercept showed anti-tumor activity in the A498 model, but not in the 786-O tumor line. However, in the combination therapy studies, dalantercept plus sunitinib slowed tumor growth to a greater extent than either agent alone or untreated tumors in both models. The data demonstrate that blocking ligand signaling through the endogenous ALK1 receptor, either alone or in combination with other anti-angiogenic therapies, is a valid strategy for treatment of renal cell carcinoma.

Dalantercept was tested in a Phase 1 study in advanced, refractory cancer patients, and was well tolerated at dose levels up to 1.6 mg/kg Q3W. Though no RCC patients were included in the Phase 1 study, one solid tumor patient had a partial response and eight patients had prolonged periods of stable disease. The dose-limiting toxicity was fluid overload, and the most frequently reported treatment-emergent adverse event (TEAEs) were fatigue, peripheral edema, nausea, anorexia, anemia, dyspnea, headache, vomiting, pyrexia, constipation, dehydration, and epistaxis. Importantly, the dalantercept side effect profile appeared largely non-overlapping with the toxicity profiles of the TKI therapies approved for the treatment of RCC. In addition in a phase one study of an anti ALK-1 antibody, a patient with RCC had a partial response. Based on its mechanism of action, the robust pharmacology model data set, and the initial safety and activity profile from the Phase 1 clinical trial, we propose to study dalantercept in combination with VEGF TKI therapy in patients with renal cell carcinoma.

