**Table 3: Management of Adverse Events Related to Dalantercept/Placebo**

Adverse Event or Abnormal Finding	Action	Dalantercept Dose Modification
Weight/peripheral edema Eventsa - Weight gain (not due to fluid retention or edema) due to improvement in health would not be considered an adverse event or abnormal finding.		
1. $\geq 3$ to $< 5\%$ increase in weight from baseline or grade 1 peripheral edema	
 
● Administer therapya as needed to maintain approximate baseline weight or to reduce edema.
 
● Hold dalantercept/placebo treatment until weight returns to baseline (<math>< 3\%</math> increase) or edema resolves.
 
	1. Upon normalization of weight or resolution of edema, dalantercept/placebo should be restarted at the same dose level.
2. $\geq 5$ to $< 10\%$ increase in weight from baseline (Grade 1) or grade 2 peripheral edema		2. Upon normalization of weight or resolution of edema, dalantercept/placebo should be reduced one dose level.
3. $\geq 10\%$ increase in weight from baseline ( $\geq$ Grade 2) or grade 3 peripheral edema	
 
● Administer therapya as needed to maintain approximate baseline weight or to reduce edema.
 
● Hold dalantercept/placebo treatment until weight returns to baseline (<math>< 3\%</math> increase) or edema resolves.
 
● A complete cardiac evaluation including chest x-ray (CXR), ECG, ECHO, troponin, and BNP should be performed if determined to be clinically necessary.
 
	3. Upon normalization of weight or resolution of edema, dalantercept/placebo should be reduced two dose levels.
Pulmonary Events		
1. A new onset of signs or symptoms of pulmonary edema (Grade 1). Signs and symptoms include but are not limited to shortness of breath, coughing up blood, end-inspiratory crackles, etc.	
 
● Administer therapya as needed.
 
● Hold dalantercept/placebo treatment until resolution of AE(s).
 
● A complete cardiac evaluation including CXR, ECG, ECHO, troponin, and BNP should be performed if determined to be clinically necessary.
 
	1. Upon resolution of AE(s), dalantercept/placebo should be reduced one dose level.

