### **10.6.3. Fluid Management Therapy**

#### **10.6.3.1. Diuretics**

Use of diuretics is allowed to maintain approximate baseline weight in the instance a weight or other fluid event occurs as described in [Table 3](#). Note that treatment with diuretics is expected for some patients during this study and such use should not be used to determine grading of hypertension.

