#### **15.4.2. Secondary Endpoints**

**Secondary endpoint:** PFS in the subgroup of the patients who had 2 or more prior lines of anticancer therapy will be analyzed similarly as the primary PFS analysis. Due to the size of the subgroup, the comparison will be tested at one-sided 0.20 significant level.

If the hazard ratio is 0.625, the same as the PFS hypothesis for overall population, the power to claim statistical significance will be 80% if the subgroup has 52 events and 70% with 34 events.

**Safety Analysis:** The safety analyses will be performed on the AT population. Adverse event incidence rates will be tabulated by System Organ Class (SOC) and preferred term and without regard to causality. The frequency of occurrence of overall toxicity, categorized by toxicity grades, will be summarized. Shift tables and change from baseline will be summarized by analyte for laboratory panels. Treatment-emergent laboratory findings will be summarized. Change from baseline and shift tables may be presented for vital sign and ECG parameters.

**Overall Survival (OS):** Another key secondary endpoint that will be estimated is OS. OS is defined as the time from randomization to death. If the trial is concluded and there is no evidence that the patient died, then the patient will be censored at the last follow-up contact visit for which the patient is documented as being alive. If the patient is lost to follow-up, all reasonable effort will be made to ascertain the patient status. Patients who discontinue from the treatment phase of the study will be followed for at least two years from randomization for OS. Median survival along with quartiles and confidence intervals will be calculated.

A Kaplan-Meier curve for survival will be displayed and 95% confidence intervals for median survival computed for each treatment arm. A stratified log-rank will be used to test the difference in OS between the two treatment arms. The hazard ratio for the OS treatment effect will be estimated using a stratified Cox model.

**Objective Response Rate (ORR):** Patients will be evaluable for ORR if they have at least one measurable lesion at baseline and at least one radiographic disease assessment after baseline. The Best Overall response rate will be estimated based on the proportion of patients evaluable for response. Exact 95% confidence intervals will be calculated.

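### The Part 2 safety analysis has no count of patients with any fluid-retention event and leaves weight summaries optional, so its tables could split or dilute the signal for dalantercept's known dose-limiting toxicity

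*Combined protocol and SAP*

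**What the plan says.** On the toxicity, section 9.2.1 reports from Phase 1: "The dose-limiting toxicity was fluid overload". Section 7.3 describes how it appeared: "Dose-dependent fluid retention manifested as peripheral edema, dyspnea, and weight gain, responded to diuretic therapy". It also reports treatment-related serious events of fluid overload and/or congestive heart failure in 3 of the 37 patients. Table 3 (section 10.6.1) manages weight gain and peripheral edema, pulmonary edema, pleural effusion and pericardial effusion under separate entries.

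On the Part 2 analysis, section 15.4.2 says: "Adverse event incidence rates will be tabulated by System Organ Class (SOC) and preferred term and without regard to causality". It continues: "The frequency of occurrence of overall toxicity, categorized by toxicity grades, will be summarized". Change-from-baseline and shift tables for vital signs and ECG are optional. Section 11.2.2 lists weight among the vital signs. ECHO is not mentioned in the Part 2 safety paragraph. For Part 1, by contrast, section 15.3 commits to summaries of vital signs, ECHO and ECG.

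On what happens to weight during treatment, Table 3 says: "Hold dalantercept/placebo treatment until weight returns to baseline", defined there as less than 3% above baseline. Section 10.6.3.1 says: "Use of diuretics is allowed to maintain approximate baseline weight". Section 7.5 lists effects of axitinib seen in more than 20% of patients, among them "weight decreased, vomiting, asthenia, and constipation". Both Part 2 arms receive axitinib.

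**The concern.** Part 2 is the only placebo-controlled part of the study, and safety and tolerability are among its secondary objectives. A harm with several presentations is tabulated term by term, across different organ classes. A patient with edema and another with pleural effusion appear on different lines, and no line gives the share of patients with any fluid event. That share is what a reader would want to compare between arms.

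Weight does not fill the gap as planned. Its summary is optional, and if produced as change by visit, it would be taken after holds and diuretics have pushed weight back toward baseline. Gains of 3 to <5% prompt a hold but carry no grade in Table 3, where grade 1 weight gain starts at 5%. Section 14.1 leaves it largely to the investigator whether an asymptomatic finding becomes an adverse event. A grouping chosen after unblinding would be open to selection, so it needs to be fixed beforehand.

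**Working it through.** **Plan's own figure.** The documents give no figure for any safety comparison. Their main design figure, 82 PFS events for about 80% power, reproduces: Φ(√(82 × 0.25) × |ln 0.625| − 1.2816) = Φ(0.846) = 80.1%. It does not bear on this point.

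The documents give 65 patients per arm and Table 3's weight bands. All event rates and weight changes below are assumptions. Power is used only as a yardstick for how visible a difference would be, since no safety test is planned.

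**1. Separate terms against a pooled category.** For two proportions at two-sided 5%, power = Φ((d − 1.96·SE0)/SE1), with SE0 = √(2·p̄(1−p̄)/65) and SE1 = √((p1(1−p1) + p2(1−p2))/65).

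| Term (assumed) | Placebo | Dalantercept | Power |
|---|---|---|---|
| Peripheral edema | 10% | 20% | 36% |
| Weight increased | 2% | 7% | 28% |
| Pleural effusion | 5% | 12% | 30% |
| Pulmonary edema/CHF | 1% | 4% | 19% |
| Dyspnea | 12% | 20% | 24% |

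Edema in full: d = 0.10, SE0 = 0.0626, SE1 = 0.0620, so Φ(−0.367) = 36%.

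If the first four terms are independent:
- Placebo: 1 − 0.90×0.98×0.95×0.99 = 17%.
- Dalantercept: 1 − 0.80×0.93×0.88×0.96 = 37%.
- Power: Φ((0.201 − 1.96×0.0780)/0.0759) = 74%.

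Adding dyspnea gives 27% against 50%, power 77%.

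If the four terms overlap fully in the same patients, the pooled rates are 10% against 20% and power stays at 36%. Pooling therefore runs from no gain to about double the best single term (74/36 ≈ 2.1). With dyspnea included under full overlap, the rates are 12% against 20% and power is 24%, below edema alone. A term with a high background rate can dilute the group.

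**2. Axitinib weight loss and the mean.** Suppose 30% of dalantercept patients and no placebo patients gain 5%. The difference in means is 0.30 × 5 = 1.5 points. If both arms also lose 3%, the means are −3.0 and −1.5, and the difference is still 1.5. What changes is the individual patient: +5 − 3 = +2%, below Table 3's 3% line.

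**3. Diuretics and the mean.** If treatment removes 80% of the gain, the difference falls to 0.30 × 5 × 0.2 = 0.3 points.

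**4. Transient gains.** Take a 9-point gain at one of six visits in 30% against 8% of patients. The expected difference at a visit is 0.22 × 9/6 = 0.33 points. A simulation (4,000 runs; between-patient SD 3 points, within-patient SD 1 point, background −2%) gives about 8% power for the mean at one visit and 67% for the share with maximum gain of 5% or more. With no background loss, the visit-mean result is essentially unchanged. With background −2% and a gain of 5 or 6 points, the 5% band has only 19% or 31% power. If the 9-point gain lasts three visits, the mid-course mean has about 47%.

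**The case against.** A reader might infer that fluid retention will be reported only as scattered terms, that axitinib weight loss and diuretics cancel the weight signal, and that the trial would therefore understate its main known harm. The documents support none of these.

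- **Only.** Toxicity by grade is planned, the optional vital-sign tables include categorical shifts, and section 15.5 plans exposure/toxicity analyses. The DMC sees unblinded safety data. Section 11.2.2 has post-dose examination findings, edema included, recorded as adverse events.
- **Cancel.** Axitinib is in both arms, so a shared loss leaves the randomized mean difference intact. Diuretics attenuate it. Edema, effusions and heart failure would still reach the adverse event tables.
- **Would understate.** Every term is still shown by arm. If 30% against 8% of patients had their event recorded under one term, that single line would have Φ((0.22 − 1.96×0.0688)/0.0661) = 90% power. Overlap is plausible, since section 7.3 presents the manifestations as one process.

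The assumed rates also have little support. The 3 of 37 serious cases came from monotherapy at 0.1 to 4.8 mg/kg, whereas Part 2 uses 0.9 mg/kg. The early combination data in section 7.4 (10 patients) list no edema, weight gain, dyspnea or effusion among events above 20%. Finally, section 15.1 defers detail to a separate SAP that is not in the text reviewed, so a grouped category there cannot be ruled out.

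These points limit the size and certainty of the concern. They do not supply a per-patient count of fluid events or a required weight summary in the protocol's Part 2 text.

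**Conclusion.** The point holds as a cheap improvement to reporting. For Part 2, the protocol defines no pooled fluid-retention category and no weight-threshold summary, and it makes vital-sign tables optional although Part 1 commits to them. The planned tables could fragment or dilute a between-arm difference in the toxicity that the protocol itself singles out. How much is lost depends on event rates and term overlap that the documents do not give. Under the assumed rates, pooling adds anything from nothing to about twice the best single term's power. Even with full overlap, it still supplies the share of patients affected. The weakness of visit-mean weight comes from gains being brief or treated, not from axitinib. Background weight loss instead limits the weight bands, which is why they should complement the pooled category.

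**What to change.** In section 15.4.2 or the SAP, before unblinding:

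(a) Pre-list a pooled fluid-retention category: peripheral edema, fluid-related weight gain, pulmonary edema, pleural effusion, pericardial effusion, and fluid overload/CHF. Report patients with at least one event by arm, with maximum grade, the difference and its 95% CI, alongside the preferred-term table. Dyspnea stays in the preferred-term table, since a less specific term can dilute the group.

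(b) Make weight a required summary: patients by maximum on-treatment gain from baseline in Table 3's existing bands (3 to <5%, 5 to <10%, 10% or more), by arm, using weight from every visit.

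(c) Tabulate newly started diuretics by arm as supportive information.

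None of this changes dosing or patient management. Weight, adverse events and concomitant medications are already collected throughout treatment. The cost is a few tables and a blinded review of the term list and of the indication for each diuretic. The weight bands will have limited sensitivity where background weight is falling, and the report should say so.

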### 9.3. Selection of Study Population

#### 9.3.1. Inclusion Criteria

Eligible patients must meet **all** of the following criteria.

1. Age  $\geq$  18 years.
2. Histologically confirmed, advanced, predominantly clear cell renal cell carcinoma (RCC).
3. **Part 1:** Progression of disease following up to three lines of prior therapy, including at least one approved VEGF receptor tyrosine kinase inhibitor (TKI) for RCC. Adjuvant therapy is permitted as one line of prior therapy.  
**Part 2:** Progression of disease following one VEGF pathway pathway inhibitor for RCC (sunitinib, pazopanib, sorafenib, bevacizumab, tivozanib, or cabozantinib) inclusive of adjuvant therapy if there was documented disease progression during treatment. Patients may have received one additional line of an approved mTOR kinase inhibitor (everolimus, temsirolimus). Prior exposure to investigational and/or approved anticancer immune therapies is permitted.
4. A minimum of 1 week since the last dose of prior therapy (a minimum of 4 weeks since anticancer immune therapy or bevacizumab +/- interferon).
5. Measurable disease that is evaluable by Response Evaluation Criteria in Solid Tumors (RECIST) v1.1 ([Appendix 1](#)).
6. Eastern Cooperative Oncology Group (ECOG) performance status of 0 or 1 ([Appendix 2](#)).
7. Life expectancy of at least 12 weeks.
8. Clinical laboratory values that meet the following criteria within 72 hours prior to study day 1:
  - Hematology (in the absence of hematopoietic growth factor support):
    - Absolute neutrophil count (ANC)  $\geq$  1,500 / $\mu$ L ( $\geq$  1.5 x 10^9 /L).
    - Hemoglobin  $\geq$  9 g/dL ( $\geq$  90 g/L).
    - Platelet count  $\geq$  100,000 / $\mu$ L ( $\geq$  100 x 10^9 /L).
  - Measured or calculated creatinine clearance, using the Cockcroft-Gault formula, ([Appendix 5](#))  $\geq$  40 mL/min.
  - Total bilirubin  $\leq$  1.2 x upper limit of normal (ULN). Patients with confirmed Gilbert's Syndrome may have bilirubin levels up to 3.0 mg/dL.
  - Aspartate aminotransferase (AST) and alanine aminotransferase (ALT)  $\leq$  2.5 x ULN ( $\leq$  5 x ULN if liver metastases are present).
  - Serum albumin  $\geq$  3.0 g/dL ( $\geq$  30 g/L).

- Sodium  $\geq 133$  mEq/L ( $\geq 133$  mmol/L).
  - Urinary protein  $< 2+$  by urine dipstick or urinalysis. If  $\geq 2+$ , then patient may be enrolled if 24-hour urine protein  $< 2$  g/24hr.

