### **12.2. Dosing Days and Interim Visits**

- All screening and study day 1 procedure results required to confirm eligibility must be obtained and reviewed prior to study drug administration. Patient eligibility for inclusion/exclusion criteria must be confirmed from these results, as applicable. Ideally, patients should be randomized within 48 hours of C1D1.
- Baseline hematology, chemistry, and urinalysis results must be reviewed prior to dosing on C1D1 but may be collected up to 72 hours prior to dosing. Baseline thyroid function may also be collected up to 72 hours prior to dosing. Therefore if the screening visit occurs within 72 hours of study day 1, the hematology, chemistry, thyroid function and urinalysis testing do not need to be repeated.
- Any non-serious AEs that occur prior to dosing in cycle 1 should be recorded in the medical history section of the CRF.
- All AEs that occur after dosing in cycle 1 should be recorded in the AE page of the CRF.

- On subsequent dosing days, all AEs and abnormal laboratory or other findings that might require modification of dosing (see [Section 10.6](#)) should be reviewed prior to dosing to ensure that the patient is still eligible to receive additional doses of dalantercept/placebo. Please note that there is an extended window of up to 5 days for the ECHO and tumor response assessment scan, when required.
- PK blood sample collection should be performed pre-dose for dalantercept/placebo and axitinib at C1D1, C2D1 and C3D1.
- Tumor response assessment scans should be performed every 6 weeks regardless of dalantercept/placebo or axitinib dosing delays through C15. After C15 tumor response assessment scans should be performed every 12 weeks regardless of dalantercept/placebo or axitinib dosing delays (e.g. C19D1, C23D1, etc.).
- The schedule of events outlines procedures through C6D1. If patients have stable or responding disease and are able to continue beyond 6 cycles of treatment, the procedures outlined for cycle 5 and 6 should be repeated until the patient comes off study (i.e. C7D1=C5D1, C8D1=C6D1, etc.). The only exception is that after cycle 5, ADA, urinalysis, thyroid function and PD biomarkers are required once every 4 cycles instead of once every 2 cycles (i.e., C9D1, C13D1, etc.).

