#### Analysis Populations:

The **All Treated (AT) Population** includes all patients who received any study drug. The AT is the population that will be used when performing the primary analysis of the primary endpoint and all safety analyses. The AT population will be analyzed according to treatment received.

The **Full Analysis Set (FAS)** includes all randomized patients. The intent-to-treat principle will be used for this study population. The FAS will be used in secondary analyses of the primary endpoint.

The **Pharmacokinetics (PK) population** will consist of all patients who received at least 1 dose of dalantercept and axitinib and have sufficient PK samples collected and assayed.

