### 15.1. Statistical Analysis Plan

Details regarding the final data analysis will be discussed in a separate Statistical Analysis Plan (SAP). The study data from Part 1 and Part 2 of the trial will be analyzed separately.

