### **15.4. Part 2 – Efficacy and Safety**

#### **15.4.1. Primary Endpoint**

**Progression free survival:** PFS is the primary endpoint in Part 2 and will be defined as the date of radiographic (also called documented) tumor progression (per RECISTv1.1) or death from any cause, whichever is earliest, minus date of randomization (or first date of dosing in Part 1 as will be implied throughout) plus one day. The term “on-study” will refer to the period from randomization until 28 days after last dose of study medication. Patients will be censored (i.e., those patients not exhibiting radiographic tumor progression or death) on the date of the last tumor assessment on-study and includes:

- Those patients discontinuing study medication due to any reason and having at least 1 radiographic tumor assessment before or on the date of discontinuation
- Those patients in whom radiographic tumor progression or death occurs following  $\geq 2$  consecutive scheduled missing radiographic tumor assessments
- Those patients given non-study antitumor medication or treatment prior to documentation of radiographic tumor progression

Patients missing baseline radiographic tumor assessments will be censored on the date of randomization. Patients with missing post-randomization radiographic tumor assessments will be censored on the date of randomization unless death occurred prior to the first and second scheduled radiographic tumor assessment, whereby death is the event.

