**Duration of Response (DR):** Duration of response is defined as the time from the first radiographic tumor response of CR or PR to the date of radiographic tumor progression or death, whichever is earliest.

**Disease Control Rate (DCR):** Disease control rate will be estimated as the proportion of patients evaluable for response who meet the criteria for CR, PR, or SD. The 95% confidence intervals of disease control rate will be calculated.

**PD Biomarkers (Exploratory):** Levels of BMP9/10, ALK1 and other relevant markers in tumor tissue and blood will be summarized, and analyzed for correlation with efficacy outcome measures.

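### ORR and DCR are computed only among patients with a post-baseline scan, and no all-randomized version is stated

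*Combined protocol and SAP*

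**What the plan says.** Under section 15.4.2, patients are "evaluable for ORR if they have at least one measurable lesion at baseline and at least one radiographic disease assessment after baseline". On the rate itself the section says: "The Best Overall response rate will be estimated based on the proportion of patients evaluable for response". For disease control: "Disease control rate will be estimated as the proportion of patients evaluable for response who meet the criteria for CR, PR, or SD". Evaluability is defined nowhere else, so the DCR denominator is naturally read as the ORR one.

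Section 15 (Analysis Populations) defines a Full Analysis Set (FAS) of all randomized patients under the intent-to-treat principle, but gives it one task: "The FAS will be used in secondary analyses of the primary endpoint". The All Treated (AT) population is assigned to the primary PFS analysis and to safety. Neither is assigned to ORR or DCR.

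Section 15.4.1 foresees patients without any post-randomization scan. For PFS they are "censored on the date of randomization unless death occurred prior to the first and second scheduled radiographic tumor assessment, whereby death is the event".

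Section 15.1 leaves analysis detail to a separate SAP, which is not part of the supplied document.

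**The concern.** Measurable disease is already an entry criterion (section 9.3.1), so the part of the rule that removes eligible patients is the post-baseline scan. Having a scan is a post-randomization outcome. A patient who dies early, withdraws, is lost to follow-up, misses the final-visit scan or is never dosed leaves the denominator.

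Early death is the clearest case. A patient who dies before the first scheduled scan is a PFS event, yet the same patient disappears from ORR and DCR. A plain treatment failure counts against the arm on one endpoint and is ignored on the other two.

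Section 9.2.2 presents ORR and DCR as secondary endpoints that support the primary result, and both are reported with 95% confidence intervals. Readers will compare the arms even without a planned test. If the arms differ in how many patients are never scanned, or why, that comparison is no longer between the randomized groups.

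**Working it through.** The plan gives no expected ORR or DCR and no expected number unscanned, so it has no figure to reproduce.

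**Inputs**
- n = 65 randomized per arm (section 9.1).
- m = patients never scanned after baseline: not given, assumed.
- r = true successes per arm: not given. Assumed equal in both arms at 16 for ORR (16/65 = 24.6%) and 50 for DCR (50/65 = 76.9%).

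**1. Effect on a single arm.** With s observed successes, the evaluable-only rate is s/(n − m). The all-randomized rate, counting unscanned patients as failures, is s/n. For s ≥ 1 the ratio is n/(n − m):

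| m | n/(n − m) |
|---|---|
| 0 | 1 |
| 1 | 65/64 = 1.016 |
| 3 | 65/62 = 1.048 |
| 7 | 65/58 = 1.121 |

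**2. Effect on the contrast, m = 7 versus 3, no true difference**

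(a) Every unscanned patient is a true failure, as with early deaths. All r successes are observed.
- Evaluable-only ORR: 16/58 − 16/62 = 27.6% − 25.8% = +1.8 points.
- Evaluable-only DCR: 50/58 − 50/62 = 86.2% − 80.6% = +5.6 points.
- All-randomized contrast: 0 for both.

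(b) Missingness is unrelated to outcome. The evaluable-only contrast is 0.
- All-randomized ORR: 24.6% × 58/65 − 24.6% × 62/65 = 22.0% − 23.5% = −1.5 points.
- All-randomized DCR: 76.9% × 58/65 − 76.9% × 62/65 = 68.6% − 73.4% = −4.7 points.

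**3. Break-even.** Let p be the share of unscanned patients who would have been successes, the same in both arms. The evaluable-only contrast is (r − 7p)/58 − (r − 3p)/62. The all-randomized contrast is (r − 7p)/65 − (r − 3p)/65 = −4p/65. The two errors are equal in size when

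(r − 7p)/58 − (r − 3p)/62 = 4p/65,

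so p = r(1/58 − 1/62) / (4/65 + 7/58 − 3/62), with denominator 0.1338.
- DCR, r = 50: p = 0.0556/0.1338 = 0.416; each rule is off by 2.6 points, in opposite directions.
- ORR, r = 16: p = 0.0178/0.1338 = 0.133; each rule is off by 0.8 points.

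Dividing p by the true rate gives 0.54 in both cases. In this example the all-randomized rule distorts the contrast less whenever unscanned patients would have succeeded at less than about 54% of the true rate.

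**The case against.** **The number unscanned may be small.** Entry requires "Life expectancy of at least 12 weeks" and ECOG 0 or 1. The first scan is due at Day 43. A final-visit scan is planned if progression has not already been confirmed (section 2, footnote 17), and every dosed patient should complete that visit (section 14.6). On never-dosed patients, section 12.2 says: "Ideally, patients should be randomized within 48 hours of C1D1". This stands: 7 of 65 (11%) is a high assumption. At m of 1 to 3 the factor is 1.02 to 1.05. On the assumed rates, with unscanned patients as failures, that is 0.4 to 1.2 points of ORR (16/64 and 16/62 against 16/65) and 1.2 to 3.7 points of DCR (50/64 and 50/62 against 50/65). No imbalance between arms is shown to be likely.

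**The conflict with PFS is limited to early deaths.** This also stands. Other patients with no post-randomization scan are censored at randomization and add no PFS information, so dropping them from the rates is in line with the PFS rule.

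**Counting missing as failure has its own bias.** True, as case (b) shows. It is a reason to report both versions. It does not justify reporting only the one that selects on being scanned.

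**The separate SAP may already hold an all-randomized or all-treated analysis.** It may. The finding is about the supplied protocol text.

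**The FAS does not match the primary PFS population, and Part 1 has no randomized patients.** Both are correct. Section 15.3 analyses Part 1 response in a similar manner to Part 2, and there the AT population, already primary for Part 1, is the natural denominator. Neither point defends selection by scan.

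**Conclusion.** The point holds for the supplied protocol. ORR and DCR rest on a denominator selected by a post-randomization outcome, and no all-randomized or all-treated alternative is stated. Relative to an all-randomized rate with unscanned patients as failures, both rates are raised by n/(n − m) whenever at least one patient is unscanned and at least one success is observed. When nobody is unscanned the versions coincide. Equal numbers unscanned, with the same outcomes, create no difference between arms under either rule; unequal numbers can move the contrast in either direction.

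The actual size cannot be known from the documents, since m and both rates are assumptions. The consequence is limited: these are secondary endpoints with no stated between-arm test, and primary PFS and OS do not change. It is worth correcting because the correction is cheap and can be fixed before the data are seen.

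**What to change.** In section 15.4.2, and in the separate SAP:

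- Make ORR and DCR in the FAS the main Part 2 estimates, counting patients with no post-baseline assessment as non-responders and as not having disease control.
- Keep the evaluable-only rates as supportive.
- Tabulate patients with no post-baseline scan by arm and reason: death, withdrawal, loss to follow-up, missed final-visit scan, never dosed.
- For Part 1, use the AT population with the same convention.

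If matching the primary PFS population matters more, an AT denominator in Part 2 also removes the selection by scan. It leaves out only never-dosed patients, although AT groups patients by treatment received.

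The cost is a few sentences and one table, with no new data. The main rates will be somewhat lower. If missingness is unequal and unrelated to outcome, the new main estimate can shift the contrast the other way, which is why both versions and the reasons should appear together.
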